6.5. Analysis Populations

6.5.1. Screen Failures

A screen failure is a subject who received information about the study, including signing an informed consent and possibly performing some study-related procedures, but was not randomized and/or did not use study product.

These subjects will neither contribute to data presentations nor be included in the statistical analyses. The number of screen failures will be included in the data disposition table.

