## **6.2** Treatment Regimen

The independent third party dispenser will be involved in providing instructions to all subjects on proper application procedures and will supervise the first application on-site. The third-party dispenser will be blinded to the treatment assignment, whether the subject is receiving active vs placebo but will know the treatment group, whether the subject was randomized to the DFD-03 group or the Tazorac group.

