### 11.2.2 Intent-to-Treat

The ITT population consists of all subjects who are randomized and dispensed study medication.

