6.5.2. Safety Population

All subjects who receive at least one confirmed dose of study product and provide any post baseline safety information will be included in the safety population. No imputation will be made for missing safety data.

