6.5.3. ITT Population

The ITT population consists of all subjects who were randomized and dispensed study medication.

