- 7. Subjects who have been treated for alcohol dependence or alcohol or drug abuse in the year prior to the Baseline Visit.
- 8. Subjects who have been in another investigational trial within 30 days of the Baseline Visit.
- 9. Subjects may not have a personal relationship with any member of the study staff or be part of the staff at the medical practice.

Listing 16.2.2.2 Subject Eligibility

	Study	Met All		
	Populations	Entrance		Subject
Subject	for Analyses	Criteria	If No, List of Inclusion/Exclusion Violations	Randomized
XXXXXX	None	Yes	I3, I4, E2	Yes
	Safety	No		No
	ITT			
	PP			
Note: ITT	= Intent-to-Trea	at. $PP = Per$	Protocol	
Program:	L-xxx.sas		Programmer: xxx	ddmmmyyyy

Protocol DFD-03-CD-008 06 Jul 2018

Listing 16.2.2.3 Protocol Deviations (PD)/Violations (PV)

	Study Popul for Analyses			Is Subject Excluded from Any Planned Analyses Population
Subject		Protocol Deviation/Violation	Major/Minor	Due to PD/PV
xxxxxx	None	xxxxxxxxxxxxxxxxxx	Major	Yes
	Safety		Minor	No
	ITT			
	PP			
Note: ITT = Intent-	to-Treat. PP = Per	r-Protocol		
Program: L-xxx.sas	3	Programmer: xxx		ddmmmyyyy

Listing 16.2.3 Study Populations

			Safety Population [1]		ITT Population [2]		PP Population [3]
	Study						
	Populations						
Subject	for Analyses	Included	Reason Excluded	Included	Reason Excluded	Included	Reason Excluded
XXXXXX	None	Yes	xxxxxxxxxxxxxxxxxxxxxxxx	Yes	xxxxxxxxxxxxxxxxxxxxxxxxxxxxx	Yes	XXXXXXXXXXXXXXXXXXXXXXXXXXXXXXXXXXXXXX
	Safety	No		No		No	
	ITT						
	PP						

Note: ITT = Intent-to-Treat. PP = Per-Protocol

- [1] All subjects who received at least one confirmed dose of study product and provided any post baseline safety information were included in the safety population
- [2] The ITT population is the primary efficacy analysis data set and consists of all subjects who were randomized and dispensed study medication.
- [3] The PP population included all subjects in the ITT population who completed the Week 12 evaluation without any major protocol violations

Program: L-xxx.sas Programmer: xxx ddmmmyyyy

Programming Notes:

- For Study Populations for Analyses column, list all study populations where study population flag in ADSL = "Y":
 - a. If SAFFL = "Y" then list Safety.
 - b. If ITTFL = "Y" then list ITT.
 - c. If PPROTFL = "Y" then list PP.
 - d. If SAFFL = "N" and ITTFL = "N" and PPROTFL = "N" then list None only.
- 2. If subject is a Screen Failure, then reason excluded from all study populations is "Screen Failure".

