- 3. If subject is not a Screen Failure and SAFFL = "N" and TR01SDT is missing then reason excluded from safety population is "No confirmed dose of study drug.".
- 4. If subject is not a Screen Failure and SAFFL = "N" and TR01SDT is not missing then reason excluded from safety population is "No post baseline safety data.".
- 5. If subject is not a Screen Failure and ITTFL = "N" then reason excluded from ITT population is "Not randomized and dispensed study drug.".
- 6. If subject is not a Screen Failure and PPROTFL = "Y" and ITTFL = "N" then reason excluded from PP population is "Not in ITT population.".
- 7. If subject is not a Screen Failure and PPROTFL = "Y" and ITTFL = "Y" then reason excluded from PP population is "Did not complete Week 12 evaluation without any major protocol violations."

Listing 16.2.4.1 Demographics and Baseline Characteristics

						Fitzpatrick Skin
Study						Type Classification
Populations 1	for				IGA Scale at	Scale at Baseline
Analyses	Age	Gender	Race	Ethnicity	Baseline [1]	[2]
None	XX	Male	White	Hispanic or Latino	0	I
Safety		Female	Black or African American Asian	Non-Hispanic or Non-Latino	1	II
ITT			American Indian or Alaska Native	Unknown	2	III
PP			Native Hawaiian or Other Pacific Islander		3	IV
			Other		4	V
						VI
	Populations : Analyses None Safety ITT	Populations for Analyses Age None xx Safety ITT	Populations for Analyses Age Gender None xx Male Safety Female ITT	Populations for Analyses Age Gender Race None xx Male White Safety Female Black or African American Asian ITT American Indian or Alaska Native PP Native Hawaiian or Other Pacific Islander	Populations for Analyses Age Gender Race Ethnicity None xx Male White Hispanic or Latino Safety Female Black or African American Asian Non-Hispanic or Non-Latino ITT American Indian or Alaska Native PP Native Hawaiian or Other Pacific Islander	Populations for AnalysesAgeGender GenderRaceEthnicityBaseline [1]NonexxMaleWhiteHispanic or Latino0SafetyFemaleBlack or African American AsianNon-Hispanic or Non-Latino1ITTAmerican Indian or Alaska NativeUnknown2PPNative Hawaiian or Other Pacific Islander3

Note: ITT = Intent-to-Treat. PP = Per-Protocol

Program: L-xxx .sas Programmer: xxx ddmmmyyyy

^{[1] 0 =} Clear; 1 = Almost Clear; 2 = Mild; 3 = Moderate; 4 = Severe

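### SAP 6.5.1 classes a randomised, dispensed non-user as a screen failure and excludes them, while SAP 6.5.3 puts the same subject in ITT

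*SAP*

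**What the plan says.** SAP 6.5.1 (Screen Failures) describes a subject who consented and may have undergone some study procedures, "but was not randomized and/or did not use study product". It then states the consequence: "These subjects will neither contribute to data presentations nor be included in the statistical analyses". Only the number of screen failures is reported, in the disposition table.

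SAP 6.5.3 says: "The ITT population consists of all subjects who were randomized and dispensed study medication". Protocol 11.2.2 has the same rule: "The ITT population consists of all subjects who are randomized and dispensed study medication". Neither asks for any use of product.

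SAP 6.5.2 defines Safety differently: "All subjects who receive at least one confirmed dose of study product and provide any post baseline safety information".

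Protocol 7.2 uses the same screen-failure definition as SAP 6.5.1 but lacks the sentence that removes these subjects from analyses.

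The programming notes to Listing 16.2.3 (SAP 11.2, Layout of Tables) bear on the same subject. Note 2 reads "If subject is a Screen Failure, then reason excluded from all study populations is" screen failure. Note 3 covers a subject who is not a screen failure, has no treatment start date and is outside Safety. It gives the lack of a confirmed dose as the reason.

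**The concern.** The joining words in the screen-failure definition make non-use sufficient on its own, whether or not the subject was randomised. For a subject who took a kit home or left the visit without applying it, SAP 6.5.1 says to exclude and SAP 6.5.3 says to include. Two programmers working from this SAP could build different ITT flags.

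The direction of the conflict matters more than its likely size. The formulation group is not blinded: Protocol 6.5.1 keeps active versus vehicle masked but leaves DFD-03 group versus Tazorac group known. The regimens also differ, a twice-daily wash-off against a once-daily cream left on overnight. A subject who declines on learning which one was assigned would, under SAP 6.5.1, leave the ITT set for a reason that may depend on the assignment. The note to Listing 16.2.3 names ITT as the main efficacy set, and an ITT set exists to prevent that kind of loss.

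**Working it through.** The plan states no figure to reproduce. The check takes each possible status and applies both rules.

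| Status of a consented subject | SAP 6.5.1 | SAP 6.5.3 / Protocol 11.2.2 | Agree? |
|---|---|---|---|
| Not randomised | Screen failure, excluded | Not ITT | Yes |
| Randomised, not dispensed, no use | Screen failure, excluded | Not ITT | Yes |
| Randomised, dispensed, no use | Screen failure, excluded | ITT | **No** |
| Randomised, dispensed, used | Not a screen failure | ITT | Yes |

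Only the third row conflicts.

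**Can the third row occur?** Yes. Protocol 7.10.2, step 9, has the dispenser assign the kit, then dispense, then supervise the first application, so dispensing precedes use. Listing 16.2.5.2 has a column asking whether a subject lost to follow-up had applied at least one dose, so the shells allow for undosed subjects.

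**Do the programming notes decide it?** No. Note 2 supplies a reason for exclusion from every population once a subject carries the screen-failure label, and the later notes apply only to subjects without that label. Note 3, however, provides for a subject with no dose date who is not a screen failure. If every non-user were a screen failure, note 3 would have little left to act on.

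**Which outputs are exposed?**
- *Safety:* requires a confirmed dose, so a non-user is already out. SAP 9 bases all safety analyses on this set, and SAP 3.2.1 makes local tolerability and TEAEs the primary endpoints.
- *PP:* requires at least 80% of expected applications (SAP 6.5.4). Zero applications fails.
- *ITT:* exposed. This covers the descriptive efficacy summaries, including the Week 12 multiple imputation (SAP 8.3), demographics (Table 14.1.3.1) and deviations (Table 14.1.2).
- *Disposition (Table 14.1.1.1):* exposed. Screen failures appear only in the Total column and randomised subjects by arm, so one subject could be counted in both rows.

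**Size per subject.** Planned arms are 50, 50, 25 and 25 (SAP 4.4).
- Active arm: 50 to 49, a loss of 1/50 = 2%.
- Vehicle arm: 25 to 24, a loss of 1/25 = 4%.
- Whole trial: 1/150 = 0.7%.

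SAP 6.4 takes percentages over all subjects in the group. Dropping one non-user from the as-observed IGA table would therefore multiply the arm's success percentage by 50/49 = 1.02 (active) or 25/24 = 1.04 (vehicle).

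**Range under an assumption.** The number of such subjects is not given. Assuming 0 to 3:
- whole trial: 0 to 3/150 = 0 to 2%;
- all in one active arm: 0 to 3/50 = 0 to 6%;
- all in one vehicle arm: 0 to 3/25 = 0 to 12%. This upper end needs all three to fall in the same small arm.

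**The case against.** The best reply is that this is loose wording, not a planned exclusion. Elsewhere the documents treat screen failures and randomised subjects as separate classes. Protocol 7.10.1 and 7.10.2 ask for a full eCRF for one and a few fields for the other, and Table 14.1.1.1 computes the ITT percentage from the number randomised. Note 3 points the same way. The dispenser "will supervise the first application on-site", and kit assignment, dispensing and first use all fall within one visit, so the window is short. The study is not powered, and efficacy is secondary and descriptive. All of this stands, and it makes the point minor. It does not remove the conflict, because the SAP 6.5.1 text still orders the exclusion.

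Three stronger readings are tempting, and the documents do not support them.

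- *That the exclusion takes precedence.* Note 2 only fills in a reason for subjects already labelled. It does not say who gets the label, and note 3 pulls the other way. Note 3 does not settle the matter for inclusion either, since it could be read as covering only subjects whose use could not be confirmed. No text ranks 6.5.1 against 6.5.3.
- *That the primary comparison is at risk.* It is not, because Safety excludes non-users in any case.
- *That this is the only place where refusal of a lotion or a cream could differ between groups.* Refusal between randomisation and dispensing is outside ITT by its own definition, and later withdrawal can also differ by formulation, although those later withdrawals remain in ITT.

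**Conclusion.** The contradiction is real and limited to subjects who were randomised and dispensed but never applied product. As written, the SAP gives two opposite instructions for them, and one of the two is a post-randomisation exclusion made with the formulation group known. It affects the ITT summaries and the disposition counts, not the primary safety analyses or PP. Each such subject is worth 2% of an active arm or 4% of a vehicle arm. That few will arise is an expectation drawn from the supervised first dose, not a documented count, and zero is possible. This is a minor correction to the SAP wording, worth making because it removes any discretion over ITT membership before the data are unblinded.

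**What to change.** In SAP 6.5.1, end the screen-failure definition at not having been randomised and delete the clause on product use. Add one sentence: subjects who were randomised and dispensed but applied no product remain in ITT and are excluded from Safety for want of a confirmed dose, the reason note 3 to Listing 16.2.3 already supplies. Notes 2 and 3 then work together without change, and Table 14.1.1.1 no longer counts anyone in both rows.

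The wording should keep the dispensing condition. A promise to retain all randomised non-users would be wider than the ITT definition.

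The cost is one deleted clause and one added sentence in the SAP, made before database lock. Protocol 7.2 can stay as it is: it carries the same definition but not the exclusion, and changing it would need an amendment agreed with the sponsor, FDA and IRB under Protocol 7.8.

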6.5.2. Safety Population

All subjects who receive at least one confirmed dose of study product and provide any post baseline safety information will be included in the safety population. No imputation will be made for missing safety data.

6.5.3. ITT Population

The ITT population consists of all subjects who were randomized and dispensed study medication.

6.5.4. Per-Protocol (PP) Population

The PP population will include all subjects in the ITT population who completed the Week 12 evaluation without any major protocol violations (i.e., any subject or investigator activity that could have possibly interfered with the therapeutic administration of the treatment or the precise evaluation of treatment efficacy).

Specifically, the PP population will include subjects in the ITT population who meet all of the following criteria:

- 1. Subject met all inclusion/exclusion criteria.
- 2. Subject did not take any prohibited concomitant medications during the evaluation period. The concomitant medication usage will be reviewed during the population determination review, remaining blinded to treatment designation, to determine prohibited medication usage that warrants exclusion from the PP population if they met the entrance criteria without any protocol violations. This review will take into consideration the timing, duration of treatment with the concomitant medication, and influence on the efficacy and safety assessments prior to deeming a prohibited concomitant medication as a protocol violation that warrants exclusion from PP.
- 3. Completed the Week 12 visit within the allowed window.
- 4. Subject was compliant with the dosing regimen. A subject will be considered compliant if the subject applied at least 80% but no more than 120% of the expected applications (168 applications expected) during the entire evaluation period.

Subjects who prematurely discontinued from the study due to documented lack of efficacy, worsening condition, or a treatment-related AE will be included in the PP population.

Other additional criteria may be added to the list to accommodate for unforeseen events that occurred during the conduct of the trial that result in noteworthy study protocol violations. These criteria will be documented with appropriate signature at the time subject populations are finalized, prior to database lock.

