#### **Methods:**

This will be a multicenter, randomized, double-blind, parallel-group, active-controlled study.

Subjects with mild to moderate facial acne vulgaris will be randomized to treatment with either DFD-03 (tazarotene) Lotion 0.1%, Tazorac (tazarotene) Cream, 0.1%, Vehicle Lotion or Vehicle Cream in a ratio of 2:2:1:1. Upon randomization, the treatment group (DFD-03 group or Tazorac group) will be known but the treatment assignment (active vs. vehicle) within that treatment group will remain blinded. During the 12-week treatment period subjects randomized to DFD-03 Lotion or Vehicle Lotion will use the study drug twice daily with approximately 12 hours between applications. Subjects randomized to Tazorac Cream or Vehicle Cream will use the study drug once daily in the evening. Subjects will be instructed to treat the entire face.

At selected site(s), subjects with acne lesions of any severity on the chest and/or back (including shoulders) may be enrolled provided they have met all inclusion criteria including mild to moderate acne on the face and have not met any exclusion criteria and will treat all areas affected with acne on the face, chest and/or back, including shoulders, if applicable. Up to 12 subjects with acne involvement on the face, chest and/or back including shoulders will be randomized to treatment with either DFD-03 (tazarotene) Lotion 0.1%, Tazorac (tazarotene) Cream, 0.1%, Vehicle Lotion or Vehicle Cream in a ratio of 2:2:1:1.

At selected site(s), subjects who are 9 to 11 years of age will be randomized to DFD-03 group only in a 1:1 ratio of DFD-03 (tazarotene) Lotion 0.1% to Vehicle Lotion. Approximately 8 subjects will be enrolled in this age range and the inclusion criteria on the number of inflammatory and non-inflammatory lesions will not be applicable to these subjects.

Safety assessments will include the investigator's assessment of local cutaneous tolerance/application site reactions on the face (dryness, non-lesional erythema, peeling, stinging, burning, and itching), vital signs (blood pressure and pulse rate), and adverse events (AEs). Local cutaneous tolerance reactions on the chest and/or back including shoulders (if applicable), will be assessed separately. Urine pregnancy tests will be performed at Screening, Baseline and at every visit through Week 12 for all female subjects. A physical examination will be performed at the Baseline and at the End of Study Visit.

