## 6.2.2 Subjects Randomized to Tazorac Cream or Vehicle Cream

Subjects will use the study product once daily in the evening. The first application will be done at the clinic supervised by the independent third party study medication dispenser and will be considered the pm dose. Subjects will then be instructed to dispense 1 gram (pea size), of study product into the palm of their hand and then apply as a thin layer over the entire face, delineated by the hairline, jaw line and ears and including the nose (avoiding the areas around the eyes, mouth and nostrils), with the tip of a finger. The applied cream on the face should be left on overnight and washed off in the morning, before applying non-medicated investigator approved sunscreen and/or moisturizer.

At the selected site(s), for subjects with acne on chest and/or back (including shoulders), an additional amount of 1-2 g of the investigational product will be similarly applied. The applied cream on the chest and/or back (including shoulders) should be left on overnight and washed off in the morning, before applying non-medicated investigator approved sunscreen and/or moisturizer.

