### 11.2.3 Per-Protocol

The PP population will include all subjects in the ITT population who complete the Week 12 evaluation without any major protocol violations (i.e., any subject or investigator activity that could have possibly interfered with the therapeutic administration of the treatment or the precise evaluation of treatment efficacy).

Specifically, the PP population will include subjects in the ITT population who meet all of the following criteria:

- 1. Subject met all inclusion/exclusion criteria.
- 2. Subject did not take any prohibited concomitant medications during the evaluation period. The concomitant medication usage will be reviewed during the population determination review, remaining blinded to treatment designation, to determine

prohibited medication usage that warrants exclusion from the PP population if they met the entrance criteria without any protocol violations. This review will take into consideration the timing, duration of treatment with the concomitant medication, and influence on the efficacy and safety assessments prior to deeming a prohibited concomitant medication as a protocol violation that warrants exclusion from PP.

- 3. Completed the Week 12 visit within the allowed window.
- 4. Subject was compliant with the dosing regimen. A subject will be considered compliant if the subject applied at least 80% but no more than 120% of the expected applications during the entire evaluation period.

Subjects who prematurely discontinue from the study due to documented lack of efficacy, worsening condition, or a treatment-related AE will be included in the PP population.

Other additional criteria may be added to the list to accommodate for unforeseen events that occurred during the conduct of the trial that result in noteworthy study protocol violations. These criteria will be documented with appropriate signature at the time subject populations are finalized, prior to database lock.

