4. STUDY DESIGN

4.1. Summary of Study Design

This was a multicenter, randomized, double-blind, parallel-group, active-controlled study. Approximately 150 subjects with mild to moderate facial acne vulgaris were randomized in a 2:2:1:1 ratio to treatment with DFD-03 (tazarotene) Lotion 0.1%, Tazorac (tazarotene) Cream, 0.1%, Vehicle Lotion, or Vehicle Cream. During the 12-week treatment period subjects randomized to DFD-03 Lotion or Vehicle Lotion used the study drug twice daily with approximately 12 hours between applications. Subjects randomized to Tazorac Cream or Vehicle Cream used the study drug once daily in the evening.

At selected site(s), subjects with acne lesions of any severity on the chest and/or back (including shoulders) may have been enrolled provided they have met all inclusion criteria including mild to moderate acne on the face and have not met any exclusion criteria and treated all areas affected with acne on the face, chest and/or back, including shoulders, if applicable. Up to 12 subjects with acne involvement on the face, chest and/or back including shoulders were randomized to treatment with either DFD-03 (tazarotene) Lotion 0.1%, Tazorac (tazarotene) Cream, 0.1%, Vehicle Lotion or Vehicle Cream in a ratio of 2:2:1:1.

Also, there were selected site(s) that enrolled approximately 8 subjects who are 9 years of age to 11 years of age. They were randomized to DFD-03 group only in a 1:1 ratio of DFD-03 (tazarotene) Lotion 0.1% to Vehicle Lotion. The total number of approximately 150 subjects in the study included up to 12 subjects with acne on the chest and/or back, and approximately 8 subjects in the age group of 9-11 years.

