9.1.3. Compliance

Compliance will be calculated for all subjects in the safety population.

Compliance (%) = $A/P \times 100$, where:

- A = Total number of applications actually applied.
- P = Total number of applications for the respective evaluation period.

Compliance will be summarized by treatment using the following statistics: n, mean, standard deviation [SD], median, minimum and maximum.

In addition, the number and percentage of subjects that have a compliance rate between 80% and 120% will be summarized by a Yes/No category. Note a subject is considered compliant with the dosing regimen if the subject has applied at least 80% but no more than 120% of the expected applications for the respective evaluation period.

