57 to 84 Days	n (%)	xx(xx.x)	xx(xx.x)	xx(xx.x)	xx (xx.x)	xx (xx.x)
> 84 Days	n (%)	xx(xx.x)	xx(xx.x)	xx(xx.x)	xx (xx.x)	xx (xx.x)
Compliance (%) [2]	n	XXX	XXX	XXX	XXX	XXX
	Mean (SD)	xxx (xx.xx)	xxx (xx.xx)	xxx(xx.xx)	xxx (xx.xx)	xxx (xx.xx)
	Median	XX.X	XX.X	XX.X	XX.X	XX.X
	Min, Max	XX, XX	XX, XX	XX, XX	XX, XX	XX, XX
Compliance (%) [3] Yes						
No	n (%)	xx(xx.x)	xx(xx.x)	xx(xx.x)	xx(xx.x)	xx(xx.x)
	n (%)	xx(xx.x)	xx (xx.x)	xx(xx.x)	xx (xx.x)	xx (xx.x)

Note: Percentages are based on the total number of subjects in each treatment group.

^[1] Days of Exposure = (stop date of study drug – start date of study drug) +1

^[2] Compliance % = A/P x 100 where A = Total number of applications actually applied. P= Total number of applications for the respective evaluation period.

^[3] A subject is considered compliant with the dosing regimen if the subject has applied at least 80% but no more than 120% of the expected applications for the respective evaluation period.

Table 14.1.5 Summary of Prior Medications Safety Population

WHO-DD ATC Class Level 1 WHO-DD ATC Class Level 2		DFD-03 Lotion	Tazorac, 0.1%	Vehicle Lotion	Vehicle Cream	Total
WHO-DD Preferred Term	Statistic	(n-xxx)	(n=xxx)	(n-xxx)	(n=xxx)	(n=xxx)
Number of Subjects with at Least One Prior	n (%)	xx (xx.xx)	xx (xx.xx)	xx (xx.xx)	xx (xx.xx)	xx (xx.xx)
Medication						
WHO-DD ATC Class Level 1	n (%)	xx(xx.xx)	xx(xx.xx)	xx(xx.xx)	xx(xx.xx)	xx (xx.xx)
WHO-DD ATC Class Level 2	n (%)	xx(xx.xx)	xx(xx.xx)	xx(xx.xx)	xx(xx.xx)	xx(xx.xx)
WHO-DD ATC Preferred Term 1	n (%)	xx(xx.xx)	xx(xx.xx)	xx(xx.xx)	xx(xx.xx)	xx (xx.xx)
WHO-DD ATC Preferred Term 2 etc.	n (%)	xx(xx.xx)	xx(xx.xx)	xx(xx.xx)	xx(xx.xx)	xx(xx.xx)
WHO-DD ATC Class Level 1	n (%)	xx(xx.xx)	xx(xx.xx)	xx(xx.xx)	xx(xx.xx)	xx(xx.xx)
WHO-DD ATC Class Level 2	n (%)	xx(xx.xx)	xx(xx.xx)	xx(xx.xx)	xx(xx.xx)	xx (xx.xx)
WHO-DD ATC Preferred Term 1	n (%)	xx(xx.xx)	xx(xx.xx)	xx(xx.xx)	xx(xx.xx)	xx(xx.xx)
WHO-DD ATC Preferred Term 2 etc.	n (%)	xx (xx.xx)	xx (xx.xx)	xx (xx.xx)	xx (xx.xx)	xx (xx.xx)

Note: Percentages are based on the total number in each treatment group

Prior medications are defined as medications with stop dates occurring before the date of first administration of the study drug. Refer to Section 6.6 in the SAP for prior medication rules.

At each level (WHO-DD ATC Class Level 1, WHO-DD ATC Class Level 2, and Preferred Term) of summarization, a subject was counted once if the subject reported one or more medications.

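### SAP 6.5.4 gives one expected count of 168 applications for every arm, so a cream subject who follows the once-daily schedule scores 40.5–59.5% and fails the per-protocol compliance criterion

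*SAP*

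**What the plan says.** SAP 6.5.4 lists four criteria for the PP population, all of which must be met. Criterion 4 asks for compliance with the dosing regimen, defined as at least 80% but "no more than 120% of the expected applications (168 applications expected) during the entire evaluation period". The number carries no arm qualifier.

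The cream regimen is described separately and repeatedly:

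- SAP 4.1: "Subjects randomized to Tazorac Cream or Vehicle Cream used the study drug once daily in the evening".
- Protocol Synopsis, Methods: "Subjects randomized to Tazorac Cream or Vehicle Cream will use the study drug once daily in the evening".
- Protocol 6.2.2, on the cream arms: "Subjects will use the study product once daily in the evening".

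The other statements of the compliance rule give no number:

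- Protocol 11.2.3: "A subject will be considered compliant if the subject applied at least 80% but no more than 120% of the expected applications".
- SAP 9.1.3, for the denominator: "P = Total number of applications for the respective evaluation period".
- Footnote 3 of the Table 14.1.4 shell, for the upper limit: "no more than 120% of the expected applications for the respective evaluation period".

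SAP 6.5.4 has one exception to its criteria: "Subjects who prematurely discontinued from the study due to documented lack of efficacy, worsening condition, or a treatment-related AE will be included". It covers early discontinuations, not completers.

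**The concern.** A single expected count cannot serve arms with different application frequencies. The figure 168 matches twice-daily use. Applied to subjects described as once daily, it doubles the denominator and places full adherence at about half of what is expected.

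Taken literally, the Tazorac Cream and Vehicle Cream columns of the PP outputs would contain only early discontinuations admitted by the exception and any subject who applied the cream far more often than once a day. The lotion columns would contain ordinary adherent completers. The two sides would not be comparable.

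The affected outputs are:

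- the 12 PP efficacy tables: IGA success, absolute lesion change, percent lesion change and CADI, each at Weeks 4, 8 and 12 (4 × 3 = 12);
- PP demographics (Table 14.1.3.2);
- the PP counts by arm (Table 14.1.1.1) and by site (Table 14.1.1.2).

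There is also a possible internal clash. If the denominator in SAP 9.1.3 is taken by regimen, the same cream subject is compliant in Table 14.1.4 and non-compliant for PP membership.

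**Working it through.** **Inputs**

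- Expected applications in the PP criterion: 168 (SAP 6.5.4).
- Compliance band: 80% to 120% (SAP 6.5.4, Protocol 11.2.3).
- Frequency: lotion arms 2 per day, cream arms 1 per day (SAP 4.1, Protocol 4 and 6.2).
- Duration: 12 weeks = 12 × 7 = 84 days.
- Week 12 window: Day 79 to Day 89 (SAP 6.7.4).
- Planned allocation: 50 DFD-03 Lotion, 50 Tazorac Cream, 25 Vehicle Lotion, 25 Vehicle Cream (SAP 4.4).
- About 150 randomized, 120 to complete (Protocol 5.1).

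**Reproducing the plan's figure.** Expected applications = applications per day × 84. Twice daily gives 2 × 84 = 168, an exact match. Once daily gives 1 × 84 = 84, which is not 168.

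**Compliant bands in whole applications**

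| Expected | 80% | 120% | Compliant range |
|---|---|---|---|
| 168 | 134.4 | 201.6 | 135–201 |
| 84 | 67.2 | 100.8 | 68–100 |

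The ranges do not overlap: 135 − 100 = 35 applications lie between the top of one and the bottom of the other.

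**Cream completers scored against 168**

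- Within 80–120% of the once-daily schedule: 68/168 = 40.5% to 100/168 = 59.5%.
- One application every day through Day 79, 84 or 89: 79/168 = 47.0%, 84/168 = 50.0%, 89/168 = 53.0%.
- The most favourable case, 120% of an 89-day once-daily period: 1.2 × 89 = 106.8, so 106/168 = 63.1%, still below 80%.
- To pass, a subject needs at least 135 applications: 135/84 = 161% of the once-daily schedule.

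**Lotion completers scored against 168.** Two applications a day through Day 79, 84 or 89 gives 158/168 = 94.0%, 168/168 = 100.0% and 178/168 = 106.0%. The rule works for these arms.

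**Number of subjects affected.** The stated allocation gives 50 + 25 = 75 cream subjects. If the 150 include the eight subjects aged 9–11, who are randomized only to the lotion arms (SAP 4.1), the figure is (150 − 8) × 3/6 = 71. At 120/150 completion, assumed equal across arms, that is 75 × 0.8 = 60 or 71 × 0.8 = 56.8, so about 57–60 cream completers.

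**The case against.** The strongest reply is that criterion 4 opens by asking for compliance with the dosing regimen. The SAP defines that regimen by arm, and the protocol states the same criterion without a number. On that view the bracketed 168 is simply the lotion figure left unlabelled, and a sensible programmer would use 84 for cream. Nearly empty cream columns would show up in Table 14.1.1.1. The populations are finalized with signature before lock, and lotion versus cream is not blinded, so the slip would probably be caught.

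Much of this is fair as a guess at intent, and detection is likely. It does not change what the text says. The sentence that defines compliance contains an explicit number, and nothing in either document limits it to the lotion arms or gives 84. The number-free statements refer to an evaluation period, not to an arm, so they do not override it. The blinded review described in 6.5.4 concerns concomitant medication. The clause on additional criteria is for unforeseen events, which the once-daily regimen was not. Using 84 without documentation would depart from the signed plan on data handling.

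A second reply is that the Duration of Treatment and Study paragraph, in the Protocol Synopsis and in the SAP's technical summary, says twice daily for 12 weeks without naming arms. Applied to everyone, that would give 168. The sentence follows the lotion dosing text and conflicts with the arm-specific cream statements. It needs reconciling with them, and no view is taken here on the regimen itself.

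Two points stand. The 168 is correct multiplication, so the fault is an inconsistency between denominator and regimen. The consequence is also limited to descriptive secondary summaries in a study not powered for significance.

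**Conclusion.** The concern holds as stated. Read as written, criterion 4 removes every cream completer who kept to 80–120% of the documented once-daily schedule. They score 40.5–59.5% where 80% is required. The rule covers 71–75 planned cream subjects, or about 57–60 completers if completion is 120/150 in every arm.

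This rests on the once-daily cream statements, which appear in several places in both documents, and on a literal reading of 168. The primary safety endpoints use the safety population and are unaffected, as are the ITT summaries. No direction of bias is claimed. It should be fixed, because the stated rule yields PP cream columns that cannot be compared with the lotion columns.

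**What to change.** In SAP 6.5.4, criterion 4, replace the single 168 with an expected count that follows each arm's documented regimen: 168 where the documents say twice daily and 84 where they say once daily. In SAP 9.1.3, state that P follows the same arm-specific regimen over the respective evaluation period.

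The revision should also say whether the fixed 12-week count or the respective-period count sets the PP flag. For completers inside the Week 12 window the two differ by at most 6% (79/84 = 0.94, 89/84 = 1.06).

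The unqualified twice-daily sentence in the duration paragraphs should be reconciled with the once-daily cream statements. Any change to the protocol's own sentence falls under Protocol 7.8 and needs sponsor, FDA and IRB agreement.

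The cost is a short revision of SAP Version 2.0 with sponsor approval before database lock, plus an arm-specific denominator in the PP flag program. No new data or protocol amendment is needed for this part. The blind is preserved, because Protocol 6.5.1 leaves lotion versus cream open. The documents give no lock date. If the database is already locked, SAP section 2 requires the departure to be noted in the study report.
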